2.2. Protocol Violations

At the discretion of the Sponsor, major protocol violations, as determined by a review of the data before locking of the study database and the conduct of statistical analyses, may result in the removal of a subject's data from the PP population. The Sponsor or designee will be responsible for producing the final protocol violation file (formatted as a Microsoft Excel file), in collaboration with Veristat and the data monitoring group as applicable; this file will include a description of the protocol violation that warrants exclusion from the PP population. This file will be finalized before hard database lock.

All protocol violations will be presented in a data listing.

3. GENERAL STATISTICAL METHODS

3.1. Sample Size Justification

The trial will enroll 24 subjects. This sample size provides ~80% power to declare superiority over historical control, assuming the true proportion of subjects who achieve the primary endpoint is 40% for the treatment arm versus 15% for the historical control, and that 90% are evaluable at Week 36 from first dose.

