2. SUBJECT POPULATION

2.1. Population Definitions

The following subject populations will be evaluated and used for presentation and analysis of the data:

- Modified Intention-to-Treat (mITT) Population: All subjects who receive at least 1 dose of VGX-3100 + EP.
- Per-protocol (PP) Population: All subjects who receive all doses of VGX-3100 + EP and have no protocol violations. Subjects excluded from the PP population will be identified and documented before locking of the study database.
- Safety Population: All subjects who receive at least 1 dose of VGX-3100 + EP.

The mITT population is the primary population for the analysis of efficacy parameters. The PP population will be considered supportive of the corresponding mITT population for the analysis of efficacy. The Safety population is the primary population for the analysis of safety endpoints.

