3.2. General Methods

All data listings that contain an evaluation date will contain a relative study day (Rel Day). Pre-treatment and on-treatment study days are numbered relative to the day of the first dose of study medication which is designated as Day 1. The preceding day is Day -1, the day before that is Day -2, etc. There is no Rel Day 0.

All output will be incorporated into Microsoft Word or Excel files, or Adobe Acrobat PDF files, sorted and labeled according to the International Council for Harmonisation (ICH) recommendations, and formatted to the appropriate page size(s).

Tabulations will be produced for appropriate demographic, baseline, efficacy, immunogenicity, and safety parameters. For categorical variables, summary tabulations of the number and percentage of subjects within each category (with a category for missing data) of the parameter will be presented. For continuous variables, the number of subjects, mean, median, standard deviation (SD), minimum, and maximum values will be presented. Summarizations will be presented by overall as applicable.

Formal statistical hypothesis testing will be performed on the primary endpoint compared with historical control at the 1-sided, 0.05 level of significance. Summary statistics will be presented, as well as 2-sided confidence intervals (CIs) on selected parameters, as described in the sections below.

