The number and percentage of subjects with response for the primary endpoint will be presented and compared to historical control. A 1-sided p-value and corresponding 1-sided 95% CI using Clopper-Pearson exact binomial methods will be presented to prove superiority over historical control. Superiority of VGX-3100 will be declared if the 1-sided p-value is <0.05 and the lower end of the CI is greater than 0.15. Primary efficacy will be analyzed separately based on qualifying lesions present at baseline and for all lesions regardless of presence at baseline.

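### Sample size, primary analysis set and responder table do not fit together: dosed subjects without a Week 36 tissue result have no defined place in the primary test, and the stated ~80% power depends on where they go

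*SAP*

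**What the plan says.** Section 3.1 sets the size: "The trial will enroll 24 subjects". It then claims: "This sample size provides ~80% power to declare superiority over historical control". It takes the true proportion achieving "the primary endpoint is 40% for the treatment arm versus 15% for the historical control", and adds the assumption "and that 90% are evaluable at Week 36 from first dose".

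The test is one-sided and exact. Section 3.2 describes the primary endpoint as "compared with historical control at the 1-sided, 0.05 level of significance", and Section 4.3.1 adds: "A 1-sided p-value and corresponding 1-sided 95% CI using Clopper-Pearson exact binomial methods will be presented". Success requires both a p-value below 0.05 and a lower limit above 0.15.

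On the analysis set, Section 2.1 states: "The mITT population is the primary population for the analysis of efficacy parameters". It defines that population as "All subjects who receive at least 1 dose of VGX-3100 + EP", with no condition that a Week 36 result exists. Section 4.3 repeats that efficacy is analysed in mITT.

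Table 2 in Section 4.3.1 makes a responder of a subject with clear histology, negative tissue PCR and no outside curative treatment. It makes a non-responder of a subject with positive histology, positive PCR or such treatment. Section 3.10, on missing data, covers only adverse event and medication dates. Section 3.2 provides a missing category in tabulations.

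**The concern.** The sample size section expects about one dosed subject in ten to have no endpoint. The analysis set keeps those subjects. The responder table has no row for them, unless they received outside curative treatment. Three parts of the same document therefore leave the denominator of the only formal hypothesis test undefined.

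Two things are at stake. If the subjects are kept and counted as failures, the trial has less power than Section 3.1 states. If they are left out, the result labelled mITT is really a completer result, which overstates response when those who dropped out did poorly. The trial is open-label and single-arm, so the choice could be made after the responses are known, and at this sample size one subject in or out of the denominator can change the conclusion.

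**Working it through.** **Inputs.** N = 24, p1 = 0.40, p0 = 0.15 and evaluable fraction 0.90 (Section 3.1); one-sided alpha 0.05 (Section 3.2); exact binomial test (Section 4.3.1).

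**Formula.** P(X ≥ r | n, p) = Σ from k = r to n of C(n,k) p^k (1−p)^(n−k). The critical value r is the smallest r with P(X ≥ r | n, 0.15) < 0.05. Power is P(X ≥ r | n, p) at the assumed true rate.

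**Step 1: the plan's own figure.** 24 × 0.90 = 21.6, so 21 or 22 evaluable.
- n = 21: r = 6 gives 0.0827 (too large) and r = 7 gives 0.0287. Power at 0.40 is 0.7998, which reproduces ~80%.
- n = 22: r = 6 gives 0.0999 and r = 7 gives 0.0368. Power at 0.40 is 0.8416.
- With the evaluable number taken as Binomial(24, 0.9), average power is 0.815.

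**Step 2: all 24 in the denominator, 40% of all 24 responding.** r = 7 gives 0.0572 (too large) and r = 8 gives 0.0199. Power at 0.40 is 0.8081, so this reading also gives about 80%.

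**Step 3: all 24 in the denominator, 40% of evaluable subjects responding, the rest counted as non-responders.** The effective rate is 0.90 × 0.40 = 0.36.
- P(X ≥ 8 | 24, 0.36) = 0.680.
- Exactly 2 missing: P(X ≥ 8 | 22, 0.40) = 0.710.
- Exactly 3 missing: P(X ≥ 8 | 21, 0.40) = 0.650.

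**Step 4: whether the choice can change the conclusion.** Take 7 responders and vary only the denominator.

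| Result | One-sided p | Lower limit | Superiority declared |
|---|---|---|---|
| 7/21 | 0.029 | 0.168 | yes |
| 7/22 | 0.037 | 0.160 | yes |
| 7/23 | 0.046 | 0.152 | yes |
| 7/24 | 0.057 | 0.146 | no |

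The chance of exactly 7 responders at a true rate of 0.40 is 0.800 − 0.650 = 0.15 with 21 evaluable, and 0.842 − 0.710 = 0.13 with 22. With 2 or 3 subjects missing out of 24, this is the probability that the handling of missing results alone decides the outcome.

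**The case against.** A reader might infer that the ~80% is an arithmetic error, or that it can be reached only by removing the non-evaluable subjects. Neither holds. The figure reproduces with 21 evaluable (0.800) and again with all 24 at 40% (0.808). Section 3.1 applies the 40% to subjects, without limiting it to evaluable ones, so a reading consistent with mITT exists. Under that reading, however, the 90% clause does no work, so the evaluable reading is the more natural one.

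A reader might also infer that 68% is the trial's power under the plan's 10% assumption. It is not, without a further rule that a missing result counts as failure, and the SAP states no such rule. The missing category in Section 3.2 suggests that these subjects remain in tabulations, but it does not say how the exact test treats them.

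Three provisions soften the problem. Section 3.9 considers supplementing subjects if more than 10% of those treated discontinue before the Week 36 procedures; 3/24 = 12.5% would pass that trigger if all three discontinued, while 2/24 = 8.3% would not. Supplementation is only to be considered. The efficacy time frame has a start (14 days before the target date) but no end, so a late biopsy still counts. Subjects who leave for outside curative treatment are already non-responders. These reduce the number of unclassified subjects. They do not classify those who remain.

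The exact size stays below 0.05 at every n examined, so for a denominator fixed in advance the type I error is controlled.

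**Conclusion.** The finding is an inconsistency between sample size, analysis set and endpoint definition. Power is about 68% (65% to 71%) if dosed subjects without a Week 36 tissue result count as non-responders. It is 80% to 84% if they are excluded, which contradicts the mITT definition, and about 81% if 40% of all dosed subjects respond. These figures rest on 24 dosed subjects, the plan's 40%, 15% and 90%, and the one-sided exact test.

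The missing rule matters more than the power figure. With 7 responders, one subject kept or dropped separates success (7/23) from failure (7/24), so the rule should be settled before the data are analysed.

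**What to change.** 1. In Table 2, add to the non-responder column: no histology or no tissue PCR result obtained in the Week 36 efficacy time frame. Make the same addition to the text definition in Section 4.3.1.
2. Define the end of that time frame in Section 3.11 and in the note to Table 2. While it stays open-ended, nobody can say when a result is missing.
3. State in Section 4.3.1 that the primary denominator is all mITT subjects. Keep the existing success rule rather than fixing a count, because the cutoff depends on the number analysed. For n = 24 the rule means 8 or more responders.
4. Give the evaluable-only result as a sensitivity analysis.
5. Restate Section 3.1: about 81% power if 40% of all treated subjects respond; about 68% if 40% of evaluable subjects respond and 10% are non-evaluable and counted as non-responders.

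The cost is SAP wording, with no additional subjects and no change to the test. The drawback is a less favourable power statement.

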3.2. General Methods

All data listings that contain an evaluation date will contain a relative study day (Rel Day). Pre-treatment and on-treatment study days are numbered relative to the day of the first dose of study medication which is designated as Day 1. The preceding day is Day -1, the day before that is Day -2, etc. There is no Rel Day 0.

All output will be incorporated into Microsoft Word or Excel files, or Adobe Acrobat PDF files, sorted and labeled according to the International Council for Harmonisation (ICH) recommendations, and formatted to the appropriate page size(s).

Tabulations will be produced for appropriate demographic, baseline, efficacy, immunogenicity, and safety parameters. For categorical variables, summary tabulations of the number and percentage of subjects within each category (with a category for missing data) of the parameter will be presented. For continuous variables, the number of subjects, mean, median, standard deviation (SD), minimum, and maximum values will be presented. Summarizations will be presented by overall as applicable.

Formal statistical hypothesis testing will be performed on the primary endpoint compared with historical control at the 1-sided, 0.05 level of significance. Summary statistics will be presented, as well as 2-sided confidence intervals (CIs) on selected parameters, as described in the sections below.

3.3. Computing Environment

All descriptive statistical analyses will be performed using SAS statistical software Version 9.3 or higher, unless otherwise noted. Medical history and adverse events will be coded using the Medical Dictionary for Regulatory Activities (MedDRA) Version 23.0. Concomitant medications will be coded using the World Health Organization (WHO) Drug Dictionary Version Mar 2016 LT.

3.4. Baseline Definitions

For all analyses, baseline will be defined as the most recent measurement before the first administration of study drug.

3.5. Methods of Pooling Data

Data will be pooled across study sites.

3.6. Adjustments for Covariates

No formal statistical analyses that adjust for possible covariate effects are planned.

3.7. Multiple Comparisons/Multiplicity

Multiplicity is not of concern for this study with a single primary efficacy endpoint.

3.8. Subpopulations

Week 64 and Week 88 exploratory efficacy endpoints will be additionally analyzed according to number of doses received (3 vs 4).

3.9. Withdrawals, Dropouts, Loss to Follow-up

If more than 10% of subjects who receive study treatment discontinue before the Week 36 primary endpoint procedures, then supplementation of study subjects will be considered.

3.10. Missing, Unused, and Spurious Data

When tabulating AE data, partial dates will be handled as follows in order to determine treatment emergence. If any of the day, month, or year is missing, the onset date will be set to the earliest date that is consistent with any non-missing date information, unless the non-missing date information is the same as study treatment start. In this case, in order to conservatively report the event as treatment-emergent, the onset date will be assumed to be the date of start of treatment. A completely missing onset date will be coded as the day of start of treatment.

A prior medication is defined as any medication that was used and has a stop date before the start of the trial (before Dose #1 on Day 0). A concomitant medication is defined as any medication that has a stop date that is on or after the date of first dose of study drug. For prior and concomitant medications, partial start dates will not be imputed, as stop dates determine prior versus concomitant. Partial stop dates will be assumed to be the latest possible date consistent with the partial date.

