4.4.2. Adverse Events

All AEs will be coded using the most current version of the MedDRA coding system and displayed in tables and data listings using system organ class (SOC) and preferred term.

Analyses of AEs will be performed for those events that are considered treatment-emergent, where treatment-emergent is defined per protocol as any AE with onset after the administration of study medication through the end of the study (i.e., study discharge).

An AESI is defined as an AE deemed related to VGX-3100 delivered with CELLECTRA™ 5PSP that requires expedited communication from the site to the Sponsor and meets any of the following criteria per the Toxicity Grade for Healthy Adults:

- Grade 3 or greater persistent administration site erythema, and/or induration recorded ≥ 2 hours immediately after study treatment
- Grade 4 or greater persistent administration site pain, tenderness recorded ≥ 2 hours immediately after study treatment
- Grade 3 or greater fewer
- Grade 3 or greater systemic symptoms, including generalized pruritus

Separate summaries of AEs will be presented for events with an onset within the first 7 and 28 days after injection and overall. The summary will include the number and percentage of subjects with any treatment-emergent AE (TEAE), any TEAE assessed by the Investigator as related to treatment, any AESI, any TEAE by Common Terminology Criteria for Adverse Events (CTCAE v4.03) grade, any SAE, any pre-treatment AE, any AE leading to discontinuation of treatment, and any AE leading to death.

In these tabulations, each subject will contribute only once (i.e., the most related occurrence or the most intense occurrence) to each of the incidences in the analysis, regardless of the number of episodes. In addition to the number of subjects that experienced at least 1 of the events, the total number of events observed across subjects will also be reported.

Summary tables by SOC and preferred term will be produced for the following:

- All TEAEs
- All TEAEs by most recent injection
- All TEAEs by severity grade
- All TEAE assessed as at least possibly related to treatment by the Investigator (i.e., treatment-related)
- All TEAEs with onset within 7 days of an injection
- All TEAEs with onset within 7 days by severity grade
- All treatment-related TEAEs with onset within 7 days of an injection
- All TEAEs with onset within 28 days of an injection
- All TEAEs with onset within 28 days of an injection by severity grade

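### The AE onset imputation in SAP 3.10 ignores the stop date, so an event with a missing or dose-1-matching onset that is known to have ended before dose 1 would be tabulated as treatment-emergent

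*SAP*

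**What the plan says.** SAP section 3.10 gives the rules for incomplete AE onset dates and says that their purpose is to settle treatment emergence when AE data are tabulated. There are three branches.

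- General rule for a partial onset: "the onset date will be set to the earliest date that is consistent with any non-missing date information".
- Exception, when the known parts coincide with treatment start: "in order to conservatively report the event as treatment-emergent, the onset date will be assumed to be the date of start of treatment".
- Onset wholly unknown: "A completely missing onset date will be coded as the day of start of treatment".

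None of the three mentions the AE stop date. The next paragraph of 3.10 does use stop dates, but only for medications: "partial start dates will not be imputed, as stop dates determine prior versus concomitant". It sets partial medication stop dates to the latest date they allow.

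Section 4.4.2 defines a treatment-emergent event as "any AE with onset after the administration of study medication through the end of the study", so onset alone decides. The same section has a separate line in the AE summary for "any pre-treatment AE". It also plans TEAE tables overall and for onsets within 7 and within 28 days of an injection. The 7-day and 28-day preferred-term rates carry exact Clopper-Pearson 95% intervals.

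**The concern.** Assigning dose 1 to an event of unknown timing is a sound conservative choice. It stops being conservative when the record itself shows that the event was over before dose 1. The rule then produces an onset later than the end of the event, which cannot be true, and labels the event treatment-emergent. Because 4.4.2 looks only at onset, no later step corrects this.

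Such events can exist. The plan reports pre-treatment AEs as a category of their own, and section 1.2.1 allows up to 10 weeks of screening, including biopsies.

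What is at stake is the accuracy of descriptive safety tables in a small single-arm study. An event that cannot be due to treatment would leave the pre-treatment line and appear as starting on the day of the first injection.

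**Working it through.** The SAP states no figure on this point, so there is none to reproduce. The check applies the 3.10 rule literally to example records and then sizes the effect.

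**Step 1: which records go wrong.** Assume, for illustration only, a first dose on 20 June 2019.

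| Known onset | Stop date | Onset under 3.10 | Result under 3.10 | With a stop-date check |
|---|---|---|---|---|
| Nothing | 10 May 2019 | 20 June 2019 | TEAE, within 7 days, onset after stop | Pre-treatment |
| June 2019 | 10 June 2019 | 20 June 2019 | TEAE, within 7 days, onset after stop | Pre-treatment |
| 2019 only | 10 May 2019 | 20 June 2019 | TEAE, within 7 days, onset after stop | Pre-treatment |
| May 2019 | 20 May 2019 | 1 May 2019 | Pre-treatment | Pre-treatment |
| 2018 only | 1 May 2019 | 1 January 2018 | Pre-treatment | Pre-treatment |

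The first three rows reach a dose-1 branch and are misclassified. The last two fall under the general rule and come out right. A complete onset date is never imputed. The error therefore needs both conditions: an onset that is wholly missing, or known only to a month or year that matches the first dose, and a stop date known to precede the first dose.

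Section 4.4.2 speaks of onset after administration, whereas the imputed value is the treatment start date itself. Section 3.10 removes any doubt, because it says that an onset set to that date is meant to count as treatment-emergent.

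**Step 2: size.** Inputs: 24 subjects (section 3.1), all assumed dosed and so in the Safety population (section 2.1); each subject counted once per SOC or preferred term (section 4.4.2).

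- Largest change in a preferred term's rate per affected subject: 1/24 = 0.0417, or 4.2 percentage points.
- Change if that subject already has a qualifying event of the same term in the window: 0.
- If the misclassified event is the only occurrence of its term, the reported 7-day rate is 1/24 = 4.2% (exact 95% CI 0.1% to 21.1%). With the stop-date check it is 0/24 = 0% (exact 95% CI 0% to 14.2%).

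The intervals show what the table would print in each case; they do not measure the error. The number of affected records cannot be derived from the SAP.

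**The case against.** The strongest defence is that the direction is deliberate: 3.10 says outright that it wants to over-report treatment emergence. That holds for events of unknown timing. It does not reach an event whose recorded end precedes the first dose, because nothing is then uncertain about its class.

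One could also argue that the phrase about non-missing date information takes in the stop date. In context it refers to the day, month and year of the onset, and the sentence on wholly missing onsets carries no condition at all.

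It is also fair that the pattern is rare. Complaints tied to a screening biopsy would often have at least a known month, and where that month precedes the dose-1 month the rule works. The planned tables of treatment-related events rest on the investigator's causality assessment, and every AE is listed by subject, so a reader of the report has other information to set beside the all-cause counts.

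A reader might infer more than the SAP supports:

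- *That the secondary 7-day safety endpoint is inflated.* Section 1.2.5.3 bases it on diary-card entries for the 7 days after each dose, and Table 1 has the cards handed out at dosing visits. An imputed onset adds nothing to a diary card.
- *That the database would need correction after lock.* The rule sets a value for tabulation; nothing in 3.10 alters the collected record.
- *That every recoded event adds 4.2 points.* Subjects count once per term, so two such events of one term in one subject add at most 4.2 points.
- *That these events would be presented as reactions to the product.* The tables concerned are all-cause TEAE counts.

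**Conclusion.** The point stands as a minor but real error in a stated rule. As written, 3.10 gives an impossible onset to an AE that has a missing or dose-1-matching onset and a stop date known to precede dose 1. That AE then moves from the pre-treatment category to the overall, 7-day and 28-day TEAE tables.

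The effect on a preferred term is between 0 and 4.2 percentage points per affected subject. This assumes that all 24 planned subjects are dosed, and the upper end applies only when the subject has no other qualifying event of that term. How many records are affected is unknown and may be none. The effect is confined to descriptive AE tables; the diary-card endpoint, the primary test and the other efficacy analyses are not affected.

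**What to change.** Add to section 3.10, before the dose-1 rules: if the AE stop date, complete or, when partial, taken at its latest possible date, is before the first dose, the AE is classified as pre-treatment and its onset is not imputed to the first dose. Add that an imputed onset may never be later than the stop date. Leave the conservative rule unchanged for every other case, including AEs with a missing stop date or one that could fall on or after the first dose.

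This extends to AEs the stop-date logic that 3.10 already uses for medications. No event that might be treatment-emergent is lost, because a partial stop date is read at its latest. The cost is one or two sentences and one condition in the AE program, with no new data.
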